We can expect that some children and young people will move to a randomised household during the observation period of the study, and that a proportion of these will move to a household randomised to a different trial arm. The Children's Commissioner (2020) found that, among children in care on 31 March 2019, most children (68%) had remained in their placement throughout the previous year, but 32% experienced one or more placement moves, 10% had experienced two or more placement moves, and 4.1% had experienced three or more. Teenagers and older children had the highest rates of placement instability. We have planned our administrative data returns to capture child and family ID codes, in order to trace the movement of children between households. We will report on the proportion of children that move between randomised households, in order to estimate the degree of trial arm 'contamination' in the current study and to predict this for a future full-scale RCT. We will also explore this in a compliance analysis (see Analysis plan).

Participants

The intervention and trial takes an inclusive approach to recruitment within households. The sample will therefore be made up of:

- Foster carers
- Kinship carers
- Foster children
- Kinship children
- Birth children, including children by blood, marriage, or legal adoption
- Other adults and children in fostering and kinship households, such as relatives and partners

Social workers also form part of fostering and kinship communities. Barnardo's will deliver services to FSWs as part of this programme, but social workers will not be randomised. Barnardo's have invited all FSWs in the three local authorities to take part in the WRAP intervention ahead of the trial, to aid programme buy-in and referrals.

Three local authorities volunteered to take part in the trial: Hull City Council; North East Lincolnshire Council; and North Lincolnshire Council.

Table 1. Information about participating local authorities

Local authority	Region	Type	Ofsted rating
Kingston Upon Hull City Council	Yorkshire and the Humber	Unitary	Requires improvement to be good (2023)
North East Lincolnshire Council	Yorkshire and the Humber	Unitary	Inadequate (2021)
North Lincolnshire Council	Yorkshire and the Humber	Unitary	Outstanding (2022)

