We will request administrative data from local authorities in March 2024. We will follow DfE SSDA903 requirements to the greatest extent possible, to minimise burden. Some data will have the foster child as the unit of analysis, and some will have the carer as the unit of analysis. We will use an Excel template for the data request that will be partially completed with demographic information about carers and children provided at randomisation. This entails routinely collected data on the care status and living arrangements of children, numbers and dates of placement changes, foster carer turnover management information (unique ID of the foster carer and step-down dates), and Strengths and Difficulties Questionnaire (SDQ) total difficulties scores for foster children (and date of the score and the unique ID of the child). We will gather SDQ scores from local authorities in March 2024, which according to published figures should be available for around 84% of looked-after children. A full breakdown of variables is provided in the spreadsheet template in Appendix 2.

For our secondary outcome of **placement changes**, we will seek data on the following variables for each foster child:

1. Number of placements since randomisation

¹⁷ Collins, J., Gibson, A., Parkin, S., Parkinson, R., Shave, D., & Dyer, C. (2012). Counselling in the workplace: How time-limited counselling can effect change in well-being. *Counselling and Psychotherapy Research*, 12(2), 84-92.

¹⁸ Maheswaran, H., Weich, S., Powell, J., & Stewart-Brown, S. (2012). Evaluating the responsiveness of the Warwick Edinburgh Mental Well-Being Scale (WEMWBS): Group and individual level analysis. *Health and Quality of Life Outcomes*, 10(1), 1-8.

¹⁹ Hamilton, E., Carr, A., Cahill, P., Cassells, C., & Hartnett, D. (2015). Psychometric properties and responsiveness to change of 15- and 28-item versions of the SCORE: A family assessment questionnaire. *Family process*, 54(3), 454-463.

2. Date of first placement change since randomisation (if applicable)
3. Nature of second placement (if applicable)
4. Reason for first placement change (if applicable)
5. Other reason for first placement change (if applicable)
6. Date of second placement change since randomisation (if applicable)
7. Nature of third placement (if applicable)
8. Reason for second placement change (if applicable)
9. Other reason for second placement change (if applicable)
10. Date of third placement change since randomisation (if applicable)

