Children in a family randomised to one trial arm are moved to a family randomised to the other trial arm	Low	Low	Data returns will enable any such children to be identified and steps taken as set out in analysis plan
Children in families randomised into the trial have already taken part in WRAP in previous delivery in Hull	Low	Low	Explore in process evaluation Hull fieldwork, set out any perceived impact in analysis and reporting

Compliance

Registration

In line with What Works for Children's Social Care requirements we will register this trial with the Open Science Framework (OSF) and update this trial registry with results at the end of the project.

Ethics

Process for obtaining ethical approval

Coram research and evaluation projects adhere to widely accepted frameworks for conducting work ethically to minimise the risk of harm to participants or wider society (Coram 2022). We obtained ethical approval from Barnardo's Research Ethics Committee on 19 December 2022.

Ethical considerations

The randomised controlled trial design

Previous research has found WRAP to have positive impacts in the USA, Ireland, China, New Zealand and Scotland, but there have been no previous evaluations, to our knowledge, of the WRAP intervention in fostering or kinship communities. We are in 'equipoise' meaning we do not know whether WRAP is effective or not in this context, making an RCT the logical next step, taking the evidence to the next level.

Well-planned and executed RCTs can establish that programmes lead to particular benefits for families, rather than other factors explaining changes. This evaluation therefore has the potential to provide the highest quality evidence to help inform future commissioning and practice.

As WRAP is not a part of usual support offered to the fostering and kinship community, those randomised into the control arm of the trial will not be denied a service that they would have otherwise received. We will ensure that information on business-as-usual support for the mental health and wellbeing of families will be made available to both the intervention and control groups, and we will ask about this in interviews and our survey of social workers.

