- Most recent Strengths and Difficulties Questionnaire total difficulties score for foster child 2
- Most recent Strengths and Difficulties Questionnaire total difficulties score for foster child 3
- Most recent Strengths and Difficulties Questionnaire total difficulties score for foster child 4
- Most recent Strengths and Difficulties Questionnaire total difficulties score for foster child 5

- Date of most recent SDQ score for foster child 1
- Date of most recent SDQ score for foster child 2
- Date of most recent SDQ score for foster child 3
- Date of most recent SDQ score for foster child 4
- Date of most recent SDQ score for foster child 5
- First name of other (non-foster) child 1
- Surname of other (non-foster) child 1
- First name of other (non-foster) child 2
- Surname of other (non-foster) child 2
- First name of other (non-foster) child 3
- Surname of other (non-foster) child 3
- First name of other (non-foster) child 4
- Surname of other (non-foster) child 4
- First name of other (non-foster) child 5
- Surname of other (non-foster) child 5
- Unique ID of other (non-foster) child 1
- Unique ID of other (non-foster) child 2
- Unique ID of other (non-foster) child 3
- Unique ID of other (non-foster) child 4
- Unique ID of other (non-foster) child 5
- DOB of other (non-foster) child 1
- DOB of other (non-foster) child 2
- DOB of other (non-foster) child 3
- DOB of other (non-foster) child 4
- DOB of other (non-foster) child 5
- Ethnic group of other (non-foster) child 1
- Ethnic group of other (non-foster) child 2
- Ethnic group of other (non-foster) child 3
- Ethnic group of other (non-foster) child 4
- Ethnic group of other (non-foster) child 5
- Gender of other (non-foster) child 1
- Gender of other (non-foster) child 2
- Gender of other (non-foster) child 3
- Gender of other (non-foster) child 4
- Gender of other (non-foster) child 5
- First name of fostering social worker
- Surname of fostering social worker
- Email address of fostering social worker

Final data return – child-level data:

- Local authority name [provided by Coram]
- Family ID [provided by Coram]
- Child ID [provided by Coram]
- Randomisation outcome 'refer for WRAP' (intervention) group or 'do not refer for WRAP (control) group [provided by Coram]
- Date of randomisation [provided by Coram]

- Date of birth of child [provided by Coram]
- Gender of child
- Ethnic group of child
- Child's postcode
- Child's legal status
- Child's care status
- Did the child receive WRAP?

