- Date of first WRAP session attended
- Number of WRAP sessions attended
- Whether WRAP was received by other members of the household, which members
- Why WRAP did not take place ('refer for WRAP group') or why WRAP did take place ('do not refer' group)? (if applicable)
- SDQ score at randomisation [provided by Coram]
- Date of SDQ at randomisation [provided by Coram]
- Second SDQ score
- Date of second SDQ score
- Version used for second SDQ score
- Number of placements since randomisation (if applicable)
- Nature of second placement (if applicable)
- Reason for first placement change (if applicable)
- Date of second placement change since randomisation (if applicable)
- Nature of third placement change since randomisation (if applicable)
- Reason for second placement change (if applicable)
- Date of third placement change since randomisation (if applicable)
- Nature of fourth placement change since randomisation (if applicable)
- Reason for third placement change (if applicable)
- Referral(s) made to CAMHS since randomisation
- Date of referral(s) to CAMHS (if applicable)
- Reasons for referrals to CAMHS (presenting issues) (if applicable)
- Comments on data (optional)

Final data return – carer-level data:

- Local authority name [provided by Coram]
- Family ID [provided by Coram]
- Child ID [provided by Coram]
- Randomisation outcome 'refer for WRAP' (intervention) group or 'do not refer for WRAP (control) group [provided by Coram]
- Date of randomisation [provided by Coram]
- Number of foster/kinship children in household at randomisation [provided by Coram]
- Number of other (birth) children in household at randomisation [provided by Coram]
- Number of foster/kinship children currently in household
- Number of other (birth) children currently in household
- Reason for changes in number of children in household (if applicable)
- Did the carer receive WRAP?
- Date of first WRAP session attended
- Number of WRAP sessions attended
- Whether WRAP was received by other members of the household, which members

- Why WRAP did not take place (if in 'refer for WRAP group') or why did WRAP take place (if in 'do not refer')
- Has the foster carer ceased fostering? (yes/no/unknown)
- Plans to cease fostering in the next year? (yes/no/unknown)
- Reasons foster carer has ceased fostering/plans to (if applicable)
- Contributing factors
- Comments on data (optional)

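### The fields listed in Annex 3 do not allow children's moves between randomised households to be traced reliably, and they contradict the main text on the first move date and the carer identifier

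*Protocol*

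**What the plan says.** **The promise.** Protocol, Randomisation, expects some children to move into a household in the other arm and explains how this will be followed: "We have planned our administrative data returns to capture child and family ID codes, in order to trace the movement of children between households". The product is stated there and again under Exploratory analysis: "We will report on the proportion of children that move between randomised households, in order to estimate the degree of trial arm 'contamination". Randomisation adds that the estimate will help to predict contamination in a full-scale trial. Table 7 (Risks) relies on the same data as its mitigation: "Data returns will enable any such children to be identified and steps taken as set out in analysis plan".

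**The fields.** Annex 3, final child-level return, has one household identifier, "Family ID [provided by Coram", and one child identifier, "Child ID [provided by Coram", both filled in by the evaluator. For a placement after the first move it asks for "Nature of second placement (if applicable" and the reason for the change. Dates are listed for the second and third changes only.

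**The main text on the same fields.** Outcome measures lists 13 placement variables. The second is "Date of first placement change since randomisation (if applicable". The same section says the return will include "foster carer turnover management information (unique ID of the foster carer and step-down dates". The carer-level return in Annex 3 lists a Child ID, but no carer ID and no date of ceasing to foster.

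**The concern.** The pre-filled Family ID identifies the household at allocation. To tell whether a child later lived in a household in the same arm, in the other arm or outside the trial, the return needs an identifier for the later household, and none is listed. If local authorities complete the form as Annex 3 describes it, a named deliverable of the pilot could not be obtained reliably.

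The missing first-change date and the carer-level identifiers are a different kind of fault: Annex 3 and Outcome measures disagree. If the annex prevails, most movers have no move date. A turnover entry would also have no listed identifier linking it to one of two carers, although the Analysis plan treats turnover at the individual carer level.

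**Working it through.** This is first a comparison of fields, then simple arithmetic for scale.

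**Step 1. Fields side by side.**

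| Item needed | Outcome measures | Annex 3 final return |
|---|---|---|
| Household at randomisation | template partly pre-filled | yes, Family ID from the evaluator |
| Identifier of each receiving household | no | no |
| Nature of, and reason for, later placements | yes | yes |
| Date of first placement change | yes (item 2 of 13) | no |
| Dates of second and third changes | yes | yes |
| Carer unique ID | yes | no (Child ID instead) |
| Step-down date | yes, in the description of the return; not in the four-item turnover list | no |

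The receiving-household identifier is absent from both lists. The other gaps are contradictions between the two.

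**Step 2. Other routes to a child's location.** Annex 3 collects each family's postal address at randomisation and the child's postcode in the final return. Separately, the endline survey asks carers for the date of birth and initials of every child then in the household. Either could be matched to randomised households. Both show at most one later address. The postcode has no reference date. The roster depends on carers responding, and the protocol expects 20% (Randomisation) or 25% (Sample Size, from a 75% response) not to. No such matching is planned.

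**Step 3. Base for the counts.** The plan's own figure reproduces: 1,269 children × 178/415 households = 544.3, against 544 stated.

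**Step 4. Movers without a date under Annex 3.** Randomisation gives one-year rates of 32% with at least one move, 10% with at least two and 4.1% with at least three.

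- At least one move: 544 × 0.32 = 174
- At least two: 544 × 0.10 = 54
- At least three: 544 × 0.041 = 22
- One move only: 544 × (0.32 − 0.10) = 120
- Share of movers with one move only: (0.32 − 0.10)/0.32 = 69%

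Counted by moves, first to third: 544 × (0.32 + 0.10 + 0.041) = 251. Of these, 544 × (0.10 + 0.041) = 77, or 31%, would be dated under Annex 3. With the Outcome measures list, all 251 would be.

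**Step 5. Carer level.** 725 carers / 415 households = 1.75. If no household has more than two approved carers, about 75% have two, so a household-level or child-level key would not identify the carer.

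**The case against.** Several points on the other side are sound.

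- Outcome measures already commits to the first-change date, carer ID and step-down dates. It also refers to a full spreadsheet template in an Appendix 2. The annex numbered 2 is power code and Annex 3 is the only field list shown, so a fuller template cannot be ruled out. The Child ID in a list headed as carer-level may be a copying slip, since carer IDs are collected at randomisation. This makes those items a reconciliation, not proof that the data will not be collected. It does not supply the receiving-household ID, which neither list contains.
- A reader might infer that contamination cannot be measured at all. The documents do not support that. Annex 3 records directly whether a child received WRAP, the first session date, the number of sessions, and why a child in the control group received it. Current residence is partly recoverable as in step 2. What is not reliably obtainable is the quantity the protocol promises, the proportion moving between randomised households.
- A reader might infer that time at risk for placement changes cannot be built. It can, crudely, from the randomisation date to the return, with the number of placements as the count. The missing date affects time to first move and its order relative to the first WRAP session; no stated model needs either.
- A reader might turn the move rates into a percentage of children crossing arms by assuming random destinations. The protocol gives no data on destinations, so such a figure has no basis.
- The specified compliance analysis uses attendance, turnover is exploratory and binary, and Table 7 rates cross-arm moves low for both likelihood and impact. All this limits the consequences. It does not remove the commitment to report the proportion.

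**Conclusion.** The point holds in limited form. The published field lists do not support reliable tracing of children between randomised households, because no receiving household is identified. Partial recovery through postcode or the survey roster would miss intermediate homes and is not planned. Annex 3 also contradicts Outcome measures on the date of first placement change, the carer ID and the step-down date.

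If Annex 3 is the form used, about 69% of movers (about 120 of 174 among 544 foster children) would have no move date. This assumes that the quoted one-year rates, which are for children in care generally, apply to these children; it counts at most three moves per child; and it ignores that follow-up for families randomised in March 2023 runs about 16 months to July 2024. The primary outcome, carer wellbeing, and the intention-to-treat comparison on it are unaffected. The loss falls on a descriptive deliverable that matters because this is a pilot meant to inform a larger trial.

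**What to change.** In the child-level return, add for each later placement the Family ID of the receiving household, or an entry such as 'not a randomised household', and restore the date of first placement change. In the carer-level return, replace the Child ID with the carer's unique ID and add the step-down date. Annex 3 then agrees with Outcome measures; the reference to Appendix 2 should be corrected at the same time.

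The cost is a few spreadsheet columns and slightly more work for local authority data teams, mostly for children who moved. That is not nothing, since Table 7 notes that these teams may struggle with data requirements, but returning to them later for missing fields would ask more of them.

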- 2% of control group households will receive WRAP despite being allocated to the 'do not receive intervention' trial arm. This is based on trial arm non-compliance from previous children's social care RCT experience.
- 95% of intervention group receive intervention. This is estimated to be high, given that all households have expressed interest in the intervention.
- Upon administration of the endline survey, 5% of carers are untraceable. This is based on previous children's social care RCT experience.
- By the point of the endline survey, 2% of households withdraw consent. This is based on previous children's social care RCT experience.
- For the primary outcome, 5% have implausible or missing values. We anticipate this being low, as we will primarily rely on an online survey for our primary outcome with set response options.
- 20% of carers do not respond to the endline survey. We anticipate that this will be low due to the use of an incentive voucher, social worker engagement in advance of survey distribution, and a schedule of reminder text messages.

Figure 2. Consort diagram showing participants' journey through the pilot RCT of Barnardo's WRAP programme

To randomise we will set up a system where local authorities provide to Coram by email a unique family ID for each family expressing interest (consenting to participate in the

programme and study). Randomisation will be stratified by local authority. This will include fields to enable us to check whether local authorities have applied the eligibility criteria correctly, before we undertake randomisations (box 1).

We anticipate randomising around 178 households using a securely stored spreadsheet pre-populated with randomisation outcomes, and return the outcomes back to local authorities and Barnardo's within 24 hours. We will do this for the stock of families in March 2023, and then on demand as needed for the in-flow of newly eligible families thereafter until early 2024.

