We have calculated the Minimum Detectable Effect Size (MDES) as 0.37 for our primary outcome. As shown in the table above, we anticipate 50:50 randomisation of 178 households, or 335 adults. Following dropout etc., we expect an analysable sample of 234 adults in 124 households. We have calculated this with a power of 0.8.

The calculations above assume a 75% response rate to the endline survey as noted in our CONSORT assumption. If we were to have a 65% endline survey response rate (202 adults) the MDES would be 0.40 (0.12-0.68) and for a 55% response rate (172 adults) this would be 0.43 (0.13-0.74).

We have used the following assumptions in our power calculation:

¹⁵ This includes, and will most likely be most influenced by, a baseline measure of the outcome.

- We have used a two-level clustered design to account for household level clustering of adult survey responses. As we are only stratifying for local authority, not randomising at local authority level, we have not used a three-level approach and will instead include local authority as a fixed effect in our models.
- We have assumed an average of 1.9 adults per foster family, including foster carers and other adults in the household. At this ratio, we expect 240 foster carers in 142 foster families. We have assumed a low to moderate ICC of 0.4. We anticipate that scores between adults in the same household will be similar in that households are exposed to some shared risk and protective factors related to wellbeing, such as socioeconomic status. However, wellbeing is subjective and influenced by individual circumstances. Our chosen ICC attempts to address this theoretical basis. Our trial's reported ICCs will be useful to inform power calculations for a future full-scale trial.
- We have assumed a considerable amount of variance as explained by covariates such as a baseline measure of the outcome, as baseline wellbeing scores are likely to be highly correlated with endline scores at an individual level.
- This is our primary outcome and therefore not subject to adjustments for multiple comparisons, so we have used an alpha of 0.05.

The MDES was calculated in R using the PowerUpR package¹⁶. The code used is provided in Annex 2.

Outcome measures

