We have made pragmatic choices, aiming to investigate the outcomes set out in the logic model while minimising burden on local authorities and participants, and maximising data quality and completeness. We have chosen to contact families using an online survey at baseline and endline, with carers without valid email addresses sent a copy by post, and reminders sent by email, post and text message as appropriate. The survey will be sent to all carers in the trial. As shown in the table below, we have scheduled prompt text messages for the baseline and endline survey, and reminder text messages for non-responders to the endline survey. We plan to keep the survey open for one month, but may extend this deadline depending on the response rate.

The baseline survey will be sent to carers shortly after families have been randomised. We therefore anticipate that most surveys will be sent in March 2023 as this is when most families will enter the programme i.e. when local authorities share contact details with Barnardo's to invite families to information sessions. However, where families become eligible or interested throughout the trial period, the survey will be sent on a rolling basis following randomisation. The endline survey will be sent in July 2024, once all WRAP Level 1 delivery has ended. This is so that the endline survey can theoretically capture any change, or lack of change, that has occurred by both adults and children/young people attending Level 1 WRAP. We anticipate that capturing outcomes at endline will pose challenges for retention and have therefore made the following plans to boost the response rate:

¹⁶ Bulus M, Dong N, Kelcey B, Spybrook J (2021). *PowerUpR: Power Analysis Tools for Multilevel Randomized Experiments*. R package version 1.1.0, <https://CRAN.R-project.org/package=PowerUpR>.

1. Foster carers and kinship carers will receive a £10 voucher upon completion of the survey at baseline and another £10 voucher at endline.
2. We will send a reminder text and email ahead of the endline survey (June 2024) to remind foster and kinship carers that they will receive the survey in July 2024.
3. We will consider phoning all randomised foster carers and kinship carers at midpoint as a courtesy to check on engagement and remind them of the endline survey. However, we will weigh this up against whether this will be too much contact and considered a nuisance.

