4. We will work with Barnardo's to explore mechanisms for reminding participants of the endline survey, including social media, via fostering social workers, and at the Keeping Connected groups.
5. We will check whether contact details for participants are up-to-date with local authority records.

In order to minimise data storage and use the most up-to-date contact details, we will obtain contact details for all randomised carers from the Barnardo's Expression of Interest form.

Table 3. Milestones for outcome measure collection

Task	Date
Referrals of families sent by Barnardo's to Coram	March-April 2023
Eligible referred families randomised by Coram, then randomisation outcomes shared with local authorities and Barnardo's	March – April 2023
Coram emails/posts baseline survey to carers (with prompt text message, if mobile phone number available)	March – April 2023
Coram randomises eligible referred families, then emails/posts baseline surveys to carers (with prompt text message, if possible)	March 2023 – March 2024
Coram sends endline survey by email/post to carers (with prompt text message, if mobile phone number available)	1 st July 2024
Coram requests administrative data from local authorities	1 st July 2024
Coram sends reminder email/text message/post to non-respondent carers	July 2024
Deadline for local authorities to send Coram administrative data request Deadline for carers to complete endline survey	31 st July 2024

The online baseline and endline surveys are hosted on Smart Survey. The prompt text message will read:

'Hi, we're Coram. You may remember agreeing to take part in our study of families in Hull and Lincolnshire. Today we emailed you a survey about your experiences as a carer: [link]. Please complete by 30th April. We will send you a £10 voucher if you complete this survey, and we will also send you another £10 voucher if you complete an additional survey in July 2024.'

The reminder text for the endline survey will read:

'Last chance to have your say! We have emailed you a survey about your experiences as a carer. Your response will help Barnardo's and local authorities to offer the best possible wellbeing support to the fostering community. We will send you a £10 voucher if you complete this survey by 31st July. The link to the survey is [link]'

We will also consider including an additional prize draw in a reminder text, dependent on the response rate.

Type	Outcome	Outcome measure	Collected from	Baseline	Endline

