Annex 2: Code used to calculate Minimum Detectable Effect Size

```
install.packages("PowerUpR")
library("PowerUpR")

#Primary outcome: Foster carer perceived peer support
#Two-Level Blocked (Fixed) Cluster-level Random Assignment Design
#Level 2 = Family, Level 1 = Adult
#Treatment and randomisation at Level 2

mdes.bcra3f2(power=.80, alpha=.05, two.tailed=TRUE,
             rho2=.4, p=.50, g2=0, r21=0.6, r22=0,
             n=1.9, J=41.3, K=3)
```

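### The baseline carer survey has no scheduled non-responder reminder, and the MDES makes no allowance for missing baseline scores

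*Protocol*

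**What the plan says.** Under Outcome measures, the protocol sends the same online survey at baseline and endline, with a £10 voucher each time. On contact it states: "we have scheduled prompt text messages for the baseline and endline survey, and reminder text messages for non-responders to the endline survey". In Table 3 the baseline rows carry a prompt text only. The one chasing row, "Coram sends reminder email/text message/post to non-respondent carers", is dated July 2024, after the endline survey goes out. The only reminder message drafted is for endline. The same section also promises reminders by several channels where appropriate, and the risk table lists reminders against poor survey response. Neither is turned into a baseline milestone.

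The baseline survey follows randomisation, so completing it is not a condition of entry.

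The attrition assumptions under Randomisation cover untraceable carers (5%), withdrawal (2%), unusable primary-outcome values (5%) and non-response: "20% of carers do not respond to the endline survey". All concern the endline or the outcome. The sample-size section adds: "The calculations above assume a 75% response rate to the endline survey as noted in our CONSORT assumption". It shows the MDES at 65% and 55% endline response but never varies baseline response. The footnote to the R² row says of the covariates: "This includes, and will most likely be most influenced by, a baseline measure of the outcome".

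**The concern.** The protocol justifies its low endline non-response partly by the planned reminder texts, so it treats reminders as a driver of response. It schedules none for baseline, and it rates the risk of too few families responding as high in both likelihood and impact. The power calculation then takes full credit for a baseline score from every analysed carer.

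A late endline answer can still be collected, but a baseline missed before WRAP begins cannot be recovered. Three planned uses depend on it:

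- the models that adjust for baseline WEMWBS;
- the balance checks on survey measures;
- the fallback for outcome data missing in relation to arm, which is last observation carried forward. With two survey waves, the value carried forward can only be the baseline score.

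Allocation is also known to the local authorities and the delivery organisation before the baseline survey goes out, so baseline response could differ by arm.

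**Working it through.** **Inputs.** From Annex 2: "mdes.bcra3f2(power=.80, alpha=.05, two.tailed=TRUE" and "rho2=.4, p=.50, g2=0, r21=0.6, r22=0", with n = 1.9 adults per household, J = 41.3 households per local authority and K = 3 (123.9 households). From the sample-size section: "we anticipate 50:50 randomisation of 178 households, or 335 adults", and 234 adults in 124 households analysable. Baseline response is not given; 75% (the endline figure) and 60% are assumptions.

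**Formula** (the blocked cluster design named in Annex 2):

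MDES = M × √[ρ(1 − R²₂)/(p(1 − p)JK) + (1 − ρ)(1 − R²₁)/(p(1 − p)JKn)], where M = t(0.975, df) + t(0.80, df) and df = K(J − 2).

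**Reproducing the plan.**

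- df = 3 × 39.3 = 117.9 and M = 2.825.
- Household term: 0.4/(0.25 × 123.9) = 0.01291.
- Carer term: 0.6 × 0.4/(0.25 × 123.9 × 1.9) = 0.00408.
- MDES = 2.825 × √0.01699 = 0.368, against 0.37 stated.
- The 202-adult and 172-adult scenarios give 0.398 and 0.432, against 0.40 and 0.43 stated.

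**Where the 234 comes from.** The 75% matches 20% non-response plus 5% unusable values. Then 335 × 0.95 × 0.98 × 0.75 = 233.9 adults, and 178 × 0.95 × 0.98 × 0.75 = 124.3 households. No factor is left for baseline non-response.

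**Effect of incomplete baseline coverage c.**

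1. *All 234 kept, missing baselines imputed.* Carer-level R² is diluted to about 0.6c (an approximation for mean imputation). At c = 0.75, R²₁ = 0.45, the carer term is 0.6 × 0.55/58.85 = 0.00561 and the MDES is 0.384. At c = 0.60, R²₁ = 0.36 and the MDES is 0.394.
2. *Complete cases, carers lost independently.* Take 90% of households as two-adult and 10% as one-adult (mean 1.9). The share of households keeping at least one adult is 0.1c + 0.9[1 − (1 − c)²]. At c = 0.75 this is 0.919, so 113.8 households averaging 1.425/0.919 = 1.55 adults: MDES 0.395. At c = 0.60 it is 0.816, so 101.1 households averaging 1.40 adults: MDES 0.426.
3. *Complete cases, whole households lost.* J becomes 41.3c: MDES 0.426 at 75% and 0.478 at 60%.
4. *No baseline score used.* R²₁ = 0 makes the carer term 0.01020: MDES 0.429.

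In cases 2 and 3, with baseline response independent of endline response, 234 × 0.75 = 175.5 adults have both scores at 75%, and 234 × 0.60 = 140.4 at 60%.

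**The case against.** The strongest reply is that the plan does not neglect the baseline. It promises reminders in general terms for both surveys, pays a baseline voucher, may extend the one-month window and lists reminders as a risk mitigation. With randomisation on demand until March 2024, one calendar date for a baseline reminder would not fit. All of this stands, so a reader should not infer that baseline non-responders will never be chased; what is missing is a scheduled step.

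A reader might also infer that the protocol assumes zero baseline non-response. It states no such thing, and the CONSORT figure is not shown; the assumption is implicit in the arithmetic.

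Nor is it certain that fewer than 234 analysed carers will have a baseline score. The baseline survey goes to all 335 adults. At 80% response, 268 would answer, and their overlap with the 234 could be anywhere from 167 (234 + 268 − 335) to 234. People who answer one survey may well answer the other, so independence is an unfavourable assumption.

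Finally, 0.43 or 0.48 might be read as the expected loss at 75% or 60% coverage. The missing-data section imputes covariates and uses complete cases as a comparison, so a missing baseline does not by itself remove a carer. The figures under imputation are 0.38 to 0.39, a modest change in a pilot.

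**Conclusion.** The point holds as a gap in the schedule and in the sample-size statement. The only dated non-responder reminder is at endline, and the MDES takes the full R² for everyone with an endline score. On assumed baseline coverage of 60% to 75%, the likely cost is an MDES of about 0.38 to 0.39 in place of 0.37. It is about 0.39 to 0.43 if only complete cases are analysed and carers drop out independently. Only the loss of whole households takes it to 0.43 to 0.48.

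Full baseline response would not by itself secure 0.37. Under Primary outcome analysis, the primary model takes only predictors significantly unbalanced between arms, and baseline WEMWBS is listed for the sensitivity models. If it is left out, the R² of 0.6 does not apply and the MDES is 0.43 whatever the baseline response.

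These figures rest on the protocol's ICC of 0.4 and family-level R² of 0, on proportional dilution of R², and on coverage rates the protocol does not supply. The case for acting is that the data cannot be recovered and the remedy is cheap, not that power collapses.

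**What to change.** - Add a baseline non-responder reminder (email, text or post) to Table 3. Set it at a fixed interval after each family's survey is sent, so that it works with rolling randomisation, before the first WRAP session where possible and on identical timing in both arms.
- Add an expected baseline response rate to the CONSORT assumptions.
- State the MDES over a range of baseline coverage: about 0.38 to 0.39 under imputation, and 0.43 with no baseline adjustment. Say which of these matches the primary model.

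The cost is a few extra messages on channels already in use and a slightly less favourable stated MDES. The pilot would also yield an observed baseline response rate to set against the planned one, which a full-scale trial would need.
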